6.3 Drop-outs, Withdrawals, Replacement Policy

If a subject withdraws from the study at any time, either at his or her request or at the Investigator's discretion, the reason(s) for withdrawal will be recorded on the relevant page of the CRF. Subjects withdrawn due to AEs will be monitored until resolution of all AEs. Subjects who withdraw from dosing will be not replaced. However, their data will still be used if they are considered part of the evaluable population, unless they state otherwise.

7 Changes from the Protocol

No changes from the protocol are planned.

[REDACTED]	■		■	[REDACTED]		
[REDACTED]	■		■	[REDACTED]		
[REDACTED]	■		■	[REDACTED]		
[REDACTED]	■		■	[REDACTED]		
[REDACTED]	■		■	[REDACTED]		
[REDACTED]	■		■	[REDACTED]		
[REDACTED]	■		■	[REDACTED]		
[REDACTED]	■		■	[REDACTED]		
[REDACTED]	■		■	[REDACTED]		
[REDACTED]	■		■	[REDACTED]		
[REDACTED]	■	[REDACTED]				
[REDACTED]	■	[REDACTED]				
[REDACTED]	■	[REDACTED]				
[REDACTED]	■	[REDACTED]				
[REDACTED]	■	[REDACTED]				
[REDACTED]	■	[REDACTED]				
[REDACTED]	■	[REDACTED]				
[REDACTED]	■	[REDACTED]				
[REDACTED]	■		■	[REDACTED]		
[REDACTED]	■	[REDACTED]	[REDACTED]	[REDACTED]		
[REDACTED]	■		■	[REDACTED]		
[REDACTED]	■		■	[REDACTED]		
[REDACTED]	■		■	[REDACTED]		
[REDACTED]	■		■	[REDACTED]		

[REDACTED]

[REDACTED]						[REDACTED]
[REDACTED]	[REDACTED]	[REDACTED]	[REDACTED]	[REDACTED]	[REDACTED]	[REDACTED]
[REDACTED]	■		■	[REDACTED]		
[REDACTED]	■		■	[REDACTED]		
[REDACTED]	■		■	[REDACTED]		
[REDACTED]	■		■	[REDACTED]		
[REDACTED]	■		■	[REDACTED]		
[REDACTED]	■		■	[REDACTED]		
[REDACTED]	■		■	[REDACTED]		
[REDACTED]	■		■	[REDACTED]		

[REDACTED]	[REDACTED]	[REDACTED]	[REDACTED]		
[REDACTED]	[REDACTED]	[REDACTED]	[REDACTED]		
[REDACTED]	[REDACTED]	[REDACTED]	[REDACTED]		
[REDACTED]	[REDACTED]	[REDACTED]	[REDACTED]		
[REDACTED]	[REDACTED]	[REDACTED]	[REDACTED]		
[REDACTED]	[REDACTED]	[REDACTED]	[REDACTED]		
[REDACTED]	[REDACTED]	[REDACTED]	[REDACTED]		
[REDACTED]	[REDACTED]	[REDACTED]	[REDACTED]		
[REDACTED]	[REDACTED]	[REDACTED]	[REDACTED]		
[REDACTED]	[REDACTED]	[REDACTED]	[REDACTED]		
[REDACTED]	[REDACTED]	[REDACTED]	[REDACTED]		
[REDACTED]	[REDACTED]	[REDACTED]	[REDACTED]		
[REDACTED]	[REDACTED]	[REDACTED]	[REDACTED]		
[REDACTED]	[REDACTED]	[REDACTED]	[REDACTED]		
[REDACTED]	[REDACTED]	[REDACTED]	[REDACTED]		
[REDACTED]	[REDACTED]	[REDACTED]	[REDACTED]		
[REDACTED]	[REDACTED]	[REDACTED]	[REDACTED]		
[REDACTED]	[REDACTED]	[REDACTED]	[REDACTED]		
[REDACTED]	[REDACTED]	[REDACTED]	[REDACTED]		
[REDACTED]	[REDACTED]	[REDACTED]	[REDACTED]		
[REDACTED]	[REDACTED]	[REDACTED]	[REDACTED]		
[REDACTED]	[REDACTED]	[REDACTED]	[REDACTED]		
[REDACTED]	[REDACTED]	[REDACTED]	[REDACTED]		
[REDACTED]	[REDACTED]	[REDACTED]	[REDACTED]		
[REDACTED]	[REDACTED]	[REDACTED]	[REDACTED]		
[REDACTED]	[REDACTED]	[REDACTED]	[REDACTED]		

[REDACTED]		[REDACTED]				
[REDACTED]		[REDACTED]				
[REDACTED]						
[REDACTED]		[REDACTED]				
[REDACTED]		[REDACTED]				
[REDACTED]			[REDACTED]	[REDACTED]		
[REDACTED]		[REDACTED]	[REDACTED]	[REDACTED]		
[REDACTED]		[REDACTED]				
[REDACTED]			[REDACTED]			
[REDACTED]						
[REDACTED]						

[REDACTED]

					[REDACTED]	[REDACTED]
[REDACTED]	[REDACTED]	[REDACTED]	[REDACTED]	[REDACTED]	[REDACTED]	[REDACTED]
[REDACTED]		[REDACTED]	[REDACTED]	[REDACTED]		
[REDACTED]		[REDACTED]	[REDACTED]	[REDACTED]		
[REDACTED]		[REDACTED]	[REDACTED]	[REDACTED]		
[REDACTED]		[REDACTED]	[REDACTED]	[REDACTED]		
[REDACTED]		[REDACTED]	[REDACTED]	[REDACTED]		
[REDACTED]		[REDACTED]	[REDACTED]	[REDACTED]		
[REDACTED]		[REDACTED]	[REDACTED]	[REDACTED]		
[REDACTED]		[REDACTED]	[REDACTED]	[REDACTED]		
[REDACTED]		[REDACTED]	[REDACTED]	[REDACTED]		
[REDACTED]		[REDACTED]	[REDACTED]	[REDACTED]		
[REDACTED]		[REDACTED]	[REDACTED]	[REDACTED]		
[REDACTED]		[REDACTED]	[REDACTED]	[REDACTED]		
[REDACTED]		[REDACTED]	[REDACTED]	[REDACTED]		
[REDACTED]		[REDACTED]	[REDACTED]	[REDACTED]		
[REDACTED]		[REDACTED]	[REDACTED]	[REDACTED]		
[REDACTED]		[REDACTED]	[REDACTED]	[REDACTED]		
[REDACTED]		[REDACTED]	[REDACTED]	[REDACTED]		
[REDACTED]		[REDACTED]	[REDACTED]	[REDACTED]		
[REDACTED]		[REDACTED]	[REDACTED]	[REDACTED]		
[REDACTED]		[REDACTED]	[REDACTED]	[REDACTED]		
[REDACTED]		[REDACTED]	[REDACTED]	[REDACTED]		
[REDACTED]		[REDACTED]	[REDACTED]	[REDACTED]		

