# 7.4 Criteria for Individual Subject Discontinuation from the Trial

Subjects may withdraw from further participation in the study at any time and for any reason without prejudice. The degree to which a subject withdraws can vary and efforts will be made to collect important safety data if feasible and the subject agrees. A subject will be considered to be withdrawn from the trial for the following reasons:

- Withdrawn consent from all treatment and follow-up
- Death
- Lost to follow-up
- Termination of the trial by the Sponsor

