#### 10.4.2 Evaluable Population

All subjects who have met the inclusion and exclusion criteria, and have completed at least 75% of the total dose required for that stage will be included in the Evaluable Population. This population will be used for the efficacy analysis.

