2.2 Study Design

This is a two-stage adaptive design. The First stage with 6 patients focuses on determining a safe dose, while stage 2 expands the study at the previously determined dose. See the Protocol section on synopsis.

Methodology: This is a Phase 1/2, open-label, prospective, single-arm study of the safety and efficacy dose-finding, systemic exposure, and device technical success of PRV111 (Cisplatin Transmucosal System) (cisplatin drug-loaded patch+PE) in subjects with oral squamous cell carcinoma (SCC) amenable to surgery.

Study Design: This is a 2-stage adaptive study. For Stage 1, up to 10 subjects will be enrolled for the purpose of 5 evaluable subjects for the 1st stage of the study to determine a safe and efficacious dose. For Stage 2, the target goal is up to 11 evaluable subjects for the efficacy analysis of the final dose. If the dose remains the same as Stage 1, Stage 2 will target 6 additional evaluable subjects but up to 21 subjects will be recruited if the dose is changed between Stage 1 and 2.

For the purpose of dose selection, tolerable dose is defined as a dose where fewer than 33% of subjects being evaluated within the safety population present with dose-limiting toxicities (DLTs). Effective dose is determined based on the evaluable population as described in the Statistical Methods section.

The 2 stages of the study are described below:

Stage 1: Up to 10 subjects will be enrolled for the purpose of 5 evaluable subjects and undergo 3 treatment applications at each of the 4 planned treatment visits. Each treatment visit will include 1 application of the PE. Starting approximately 5 minutes after application

of the PE, 1 or 2 patches (depending on tumor size) will be applied. A total of 3 treatment applications of patches will occur. These successive applications will span approximately 35 minutes. The 3 applications provide a total of 6 mg of cisplatin per visit (12 mg if 2 patches are applied at the same time). The 4 treatment visits will be separated by 2 to 4 days (at least 48 hours).

The following decisions will be made based on safety and efficacy of the dose:

Dosing Rules for Stage 1:

- 1) If fewer than 2 subjects experience DLTs, then the following scheme will be considered for stage 2 dosing:
 - a. If fewer than or equal to 2 of the evaluable subjects have a response (Defined in the efficacy table) the dose will be escalated from 3 to 5 treatment applications per treatment visit for Stage 2.

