2.12 Study Endpoints

2.12.1 Primary Endpoints

The primary endpoints for the study involve determination of a safe and efficacious dose of PRV111 (Cisplatin Transmucosal System) (cisplatin drug-loaded patch + PE) under the conditions of the trial. Therefore, the primary endpoint is based on the incidence of DLTs and tumor volume change from baseline (CFB).

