5.3.1 Safety Population

All subjects who have at least 1 PRV111 patch applied will be included in the Safety Population.

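### SAP 6.3 lets an evaluable subject who stops dosing have already-collected efficacy data left out on request, an exclusion found in neither population definition nor declared as a change from the Protocol

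*SAP*

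**What the plan says.** SAP 6.3 first states "Subjects who withdraw from dosing will be not replaced" and then "However, their data will still be used if they are considered part of the evaluable population, unless they state otherwise". It sets no deadline for the subject's request, does not limit the kind of data, and does not separate data already held from data still to be collected.

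The population definitions contain no such condition. Under Protocol 10.4.2, eligible subjects who "have completed at least 75% of the total dose required for that stage will be included in the Evaluable Population" form the efficacy population. SAP 5.2.2 repeats this and equates 75% with three of the four application visits. For safety, SAP 5.3.1 says "All subjects who have at least 1 PRV111 patch applied will be included in the Safety Population". Where Protocol 7.4 mentions the subject's agreement, it concerns further collection: "efforts will be made to collect important safety data if feasible and the subject agrees".

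SAP section 7 states "No changes from the protocol are planned". SAP 2.2 describes an "open-label, prospective, single-arm study".

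**The concern.** Membership of the Evaluable Population should be fixed by eligibility and dose received. SAP 6.3 adds a third condition, the subject's wish, which can be expressed after tumor measurements are known. The schedule of events records tumor volume and response category at Visits 2, 3, 4 and 5. A subject who stops after Visit 3 is therefore evaluable and already has response assessments on file, which both subject and investigator know.

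Nothing in the SAP counts a removed subject as a non-responder. SAP 6.2 says that unretrievable efficacy data will be imputed and then, under a non-responder imputation heading, that no imputation will be applied. With about 11 subjects in the primary analysis, one exclusion can matter.

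**Working it through.** **Inputs.** Null rate 0.30, alternative 0.85, n1 = 5, r1 = 2, N = 11, R = 6, alpha 0.018, power 96.44% (Protocol 10.2). Success means at least 7 responders among up to 11 evaluable subjects (SAP 3.1.2). A one-sided exact binomial test at 0.018 is stated separately (Protocol 10.2, SAP 5.1). The documents give no opt-out rate, so k = 1 to 3 removals is an assumption.

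**Step 1: reproduce the plan.** With X ~ Bin(5, p) in Stage 1 and Y ~ Bin(6, p) in Stage 2, the probability of success is the sum over x = 3, 4, 5 of P(X = x) × P(Y ≥ 7 − x).

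At p = 0.30: 0.1323 × 0.0705 + 0.02835 × 0.2557 + 0.00243 × 0.5798 = 0.0180. At p = 0.85 the same sum gives 0.9644. Both of the plan's figures reproduce.

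**Step 2: removal without further enrolment, 7-response rule.** Deleting a non-responder leaves the number of responders unchanged. Six responders remain a failure and seven remain a success, so this rule is not affected.

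**Step 3: removal with enrolment continued to 11 evaluable.** Assume the dose is unchanged after Stage 1, and that up to k Stage 2 non-responders are removed, each followed by a further subject. Success then needs at least 7 − x responders among 6 + k Stage 2 subjects, so Y ~ Bin(6 + k, 0.30):

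| k | P(Y ≥ 4) | P(Y ≥ 3) | P(Y ≥ 2) | Type I error |
|---|---|---|---|---|
| 0 | 0.0705 | 0.2557 | 0.5798 | 0.018 |
| 1 | 0.1260 | 0.3529 | 0.6706 | 0.028 |
| 2 | 0.1941 | 0.4482 | 0.7447 | 0.040 |
| 3 | 0.2703 | 0.5372 | 0.8040 | 0.053 |

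For k = 1: 0.1323 × 0.1260 + 0.02835 × 0.3529 + 0.00243 × 0.6706 = 0.0167 + 0.0100 + 0.0016 = 0.0283.

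**Step 4: removal under the exact test at 0.018.**

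- P(Bin(11, 0.30) ≥ 7) = 0.0173 + 0.0037 + 0.0005 + smaller terms = 0.0216, above 0.018.
- P(Bin(10, 0.30) ≥ 7) = 0.0090 + 0.0014 + 0.0001 + smaller terms = 0.0106, below 0.018.

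The test needs 8 responders out of 11 but only 7 out of 10, so removing one non-responder from 7/11 changes its result.

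**Step 5: safety.** SAP 5.3 uses the Safety Population for all safety summaries, SAP 5.3.1 admits anyone with at least one patch, and SAP 2.2 judges tolerability within that population. None of these depends on evaluability or on a subject's request. SAP 6.3 refers to withdrawn subjects' data without restricting it to efficacy, so the wording conflicts with these sections.

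**The case against.** The clause is narrow. It concerns subjects who stop dosing, and to be evaluable they must have completed three of four visits. In practice it reaches those who stop after the third. The request is the subject's to make, not the investigator's or the sponsor's. The final response is measured from Visit 1 to Visit 5, at least 72 hours after the last treatment, so it may not exist when dosing stops. All of this stands, and it limits how often the clause could operate. It does not make a request independent of the interim measurements, and the clause would also allow a request made after Visit 5.

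The change from 7/11 to 7/10 owes its existence to another mismatch: 0.018 is the two-stage error, whereas a single-stage exact test of 7/11 gives 0.0216 with no withdrawal at all. Under the 7-response rule 7/11 already succeeds. That is correct, and Step 4 therefore applies only if the exact test decides.

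The no-replacement statements (Protocol 7.7, SAP 2.8 and 6.3) could be read as ruling out Step 3. However, both documents enrol toward an evaluable target: up to 10 subjects for 5 evaluable in Stage 1, and in Protocol 6.1 up to 21 more for 11 evaluable at the final dose. If non-replacement did hold, the analysis could end with fewer than 11, which is the setting of Step 4.

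A reader might also infer that toxicities of withdrawn, non-evaluable subjects are discarded, so that 2 of 5 with a DLT becomes 1 of 4. The documents do not support this. SAP 6.3 says when data will still be used, not that they are used in no other case. Besides the sections in Step 5, Protocol 8.4 keeps subjects with a DLT in the study for data collection.

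Finally, whether a subject may forbid use of data already held is partly a matter of consent terms, which were not available for this review.

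**Conclusion.** The point holds for efficacy. SAP 6.3 states an exclusion that the Protocol does not contain and that SAP section 7 does not declare, and in an open-label trial it can depend on the response observed to date.

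The type I error of 0.028, 0.040 or 0.053 assumes an unchanged dose, 1 to 3 removals that are all Stage 2 non-responders, and enrolment continuing to 11 evaluable. The move from p = 0.0216 to p = 0.0106 assumes that the exact test at 0.018 governs. If the 7-response rule governs and no further subjects are enrolled, removing non-responders cannot turn failure into success.

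Three stronger readings should not be drawn: that non-responders are known to be likelier to withdraw, that the final response is always known at withdrawal, or that DLTs will be removed. The documents give no evidence for the first, the visit schedule contradicts the second, and for the third there is only a conflict of wording to reconcile.

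**What to change.** Replace the sentence in SAP 6.3 with:

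> All data collected up to withdrawal are kept and analysed in every population whose definition the subject meets (Safety: at least 1 patch; Evaluable: Section 5.2.2). Evaluability and subject request do not affect Safety or DLT counts.

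Add that, if the consent terms or law require deletion, the subject is listed, still counts toward the evaluable target so that no extra subject is enrolled in their place, and the primary result is also reported with that subject as a non-responder. Check the wording against the consent form before adopting it.

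The cost is a short change to the SAP. The design's alpha of 0.018 and power of 96.44% are unchanged. The downside is that the reported response rate may be slightly less favourable.

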8.2 Appendix 2: ECOG Performance Status (ECOG PS)

Performance status will be assessed using ECOG PS at Baseline for inclusion criterion.

Grade	ECOG PS
0	Fully active, able to carry on all pre-disease performance without restriction
1	Restricted in physically strenuous activity but ambulatory and able to carry out work of a light or sedentary nature, e.g., light house work, office work
2	Ambulatory and capable of all self-care but unable to carry out any work activities; up and about more than 50% of waking hours
3	Capable of only limited self-care; confined to bed or chair more than 50% of waking hours
4	Completely disabled; cannot carry on any self-care; totally confined to bed or chair
5	Dead

8.3 Appendix 3: Common Terminology Criteria for Adverse Events (CTCAE)

CTCAE Grade refers to the severity of the AE. The CTCAE displays Grades 1 through 5 with unique clinical descriptions of severity for each AE based on this general guideline:

Grade	Severity Description
1	Mild; asymptomatic or mild symptoms; clinical or diagnostic observations only; intervention not indicated.
2	Moderate; minimal, local or noninvasive intervention indicated; limiting age-appropriate instrumental ADL*.
3	Severe or medically significant but not immediately life-threatening; hospitalization or prolongation of hospitalization indicated; disabling; limiting self-care ADL**.
4	Life-threatening consequences; urgent intervention indicated.
5	Death related to AE

*Instrumental ADL refer to preparing meals, shopping for groceries or clothes, using the telephone, managing money, etc.

**Self-care ADL refer to bathing, dressing and undressing, feeding self, using the toilet, taking medications, and not bedridden.
